7.0 STUDY OUTCOMES

The ABLATE PAS will utilize a 48 hour Holter, Zio	o™ Patch or PPM interrogation performed at follow up
t	to assess efficacy (i.e. freedom from AF). Additionally,
secondary efficacy outcomes will be reported	post-operatively. The Holter Monitor,
Zio™ Patch or PPM interrogation data shall be re	eviewed by an independent Core Laboratory

The following are the primary and secondary efficacy outcomes for this ABLATE Post-Approval Study:

7.1 Primary Efficacy Outcome

The proportion of patients free from AF (i.e. no episodes lasting > 30 continuous seconds duration of either Atrial Fibrillation, Atrial Flutter or Atrial Tachycardia) while off Class I and III antiarrhythmic drugs for at least 4 weeks (except amiodarone which must be 12 weeks) prior to assessment), as determined by an independent core lab assessment of 48 hour Holter, Zio™ Patch or PPM interrogation recording performed

7.2 Secondary Efficacy Outcome

The proportion of patients free from AF, regardless of AAD usage (i.e. no episodes lasting > 30 continuous seconds duration of either Atrial Fibrillation, Atrial Flutter or Atrial Tachycardia), as determined by an independent core lab assessment of 48 hour Holter, Zio™ Patch or PPM interrogation recording performed

7.3 Primary Safety Outcome

The proportion of patients with any serious device or ablation procedure-related adverse event within 30 days post-procedure or hospital discharge (whichever is later).

7.4 Secondary Safety Outcomes

In addition to the primary safety outcome discussed above the following safety outcomes will be evaluated:

- Composite major adverse event: Serious adverse events occurring post-operatively within 30 days of procedure or hospital discharge (whichever is later) including:
 - o Death (includes deaths after 30 days or hospital discharge if death is procedure related).
 - Stroke (resulting in significant permanent disability)
 - o TIA
 - o Myocardial infarction, and
 - Excessive bleeding (requiring >2 units of blood replacement and surgical intervention).

All serious adverse events that are reported in the study shall be summarized and reported. The events shall be summarized at each follow up interval based upon level of seriousness (serious vs. non-serious) and attribution (device, ablation procedure, procedure to address structural heart disease, co-morbid condition, etc.) to provide a complete profile of the acute and long-term safety of the device and procedure.

- Device and ablation procedure-related serious adverse events summarized and reported by type of surgical procedure (i.e. surgical procedure to address structural heart disease).
- Permanent Pacemaker Implantation (PPM) occurring within 30 days post procedure will be summarized and reported by reason for PPM implantation (i.e., sinus node dysfunction, AV node, etc.).

8.0 DEVICE DESCRIPTION, POTENTIAL RISK BENEFITS & STUDYJUSTIFICATION

The	e approved AtriCure Synergy Ablation System devices	

Refer to the Instructions for Use (IFU) for descriptions, indications for use, contraindications, system preparation, precautions and warnings.

8.1 Potential Risks and Benefits

A summary of the risks and benefits of the AtriCure system are outlined in the product Instructions for Use (IFU)

AtriCure Inc. Page 18 of 46

9.0 ELIGIBILITY CRITERIA

9.1 Subject Inclusion Criteria

In order to be eligible to participate in this study, a subject must meet all of the following criteria:

- Age ≥ 18 years
- History of a non-paroxysmal form of atrial fibrillation as defined by the HRS/EHRA/ECAS Consensus Statement.
 - Persistent AF shall be defined as continuous AF that is sustained beyond seven days. Episodes of
 AF in which a decision is made to electrically or pharmacologically cardiovert the patient after >
 48 hours of AF, but prior to 7 days, should also be classified as persistent AF episodes.
 - Longstanding persistent AF shall be defined as continuous AF of greater than 12 months duration. The performance of a successful cardioversion (sinus rhythm >30 seconds) within 12 months of an ablation procedure with documented early recurrence of AF with30 days should not alter the classification of AF as long-standing persistent.

Note: For both types of AF, two (2) electrocardiograms (e.g. 12-lead ECG, Holter, event monitor, Implantable Loop Recorder (ILR), Pacemaker, Zio^{TM} Patch, etc.) documenting AF, with electrocardiograms taken at least 7 days apart, for subjects with sustained AF \geq 7 days. Holter, event monitor, ILR, Zio^{TM} Patch or pacemaker recordings need to show continuous AF.

- Subject is scheduled to undergo elective open cardiac surgical procedure(s) to be performed on cardiopulmonary bypass for one or more of the following: Coronary Artery Bypass Grafting, Mitral valve repair or replacement, Aortic valve repair or replacement, Tricuspid valve repair or replacement. In conjunction with these procedures patent foramen ovale (PFO) or atrial septal defect (ASD) repair are allowed.
- The patient (or their legally authorized representative) agrees to participate in this study by signing the IRB approved informed consent form.
- Willing and able to return for scheduled follow-up visits.

9.2 Subject Exclusion Criteria

A potential subject who meets any of the following criteria will be excluded from participation in this study:

- Stand alone AF without indication(s) for concomitant cardiac surgery.
- Need for emergent cardiac surgery (i.e. cardiogenic shock).
- Preoperative need for an intra-aortic balloon pump or intravenous inotropes.
- Pregnancy or desire to get pregnant for the duration of the study (concomitant surgical procedure through the thirty six (36) month follow-up period).
- Enrolled in another clinical trial that could confound the results of this study.

10.0 REASONS FOR WITHDRAWAL

A study subject will be discontinued from participation in the study if:

- The investigator feels that the subject can no longer fully comply with the requirements of the study or if any of the study procedures would not be in the best interest of the subject. Non-compliance will be clearly documented in the subject's source documentation (i.e., progress notes, medical records, etc.)
- The subject is lost to follow up. A subject will be considered "lost to follow-up" and terminated from the study when all of the following criteria have been met:
 - Failure to complete the remainder of the scheduled study visits without due cause; and
 - Documentation of three unsuccessful attempts to contact the subject via telephone and by certified mail.
- The subject wishes to withdrawn their consent for participation in the study.

[figure not shown]
11.0 TREATMENT OF SUBJECTS

[figure not shown]
The aim of all AF treatment is a complete bi-atrial MAZE IV procedure.	
Based on the type of concomitant surgery or patient presentation, it is recognized that there may be	
situations in which some lesions are not able to be performed safely.	

[figure not shown]
Mandatory Lesions - A protocol deviation will be documented for any **mandatory** left sided lesion that is either not performed or performed without utilizing the energy source(s) as described in Table 4.

Recommended and Optional Lesions - - A clinical justification must be provided for any **recommended or optional lesions** that are either not performed or performed using an energy source that is different than the energy source(s) as described in Table 4. Protocol deviations will be required if a clinical justification is not provided. . Note: Surgeon's preference is not considered to be a clinical justification.

The investigator should refer to the IFU for details on the product, preparation and usage.

12.1 Repeat Ablation and/or Cardioversion Procedures

All information regarding any repeat catheter ablations (reason for the re-do as well as location) or any cardioversions will be collected and documented in the CRF. The most prevalent post-procedure rhythm will also be documented and recorded in the CRF.

12.2 Permanent Pacemaker Implantations (PPM)

Information regarding PPM implantation within 30 days of the procedure will be collected and documented in the CRF, including time of implant and reason.

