13.3	EVENTS THAT DO NOT REQUIRE REPORTING TO THE SPONSOR	26
13.4	Serious Adverse Events	27
14.0	CLINICAL EVENTS COMMITTEE (CEC)	27
15.0	MEDICAL DEVICE REPORTING	28
15.1	Manufacturer Reporting Requirements	28
16.0	STATISTICAL CONSIDERATIONS	28
16.1	STATISTICAL OVERVIEW	28
16.2	Analysis Populations	28
16.3	SAMPLE SIZE CALCULATIONS AND ASSUMPTIONS	29
16.4	Safety	29
16.5	EFFICACY	30
16.6	Statistical Analyses	30
17.0	QUALITY CONTROL AND QUALITY ASSURANCE	31
17.1	Protocol Deviations	31
17.2	INVESTIGATOR / INVESTIGATIONAL SITE TRAINING	32
17.3	Monitor Training	32
17.4	Study Monitoring	32
17.5	SITE MONITORING	32
17.6	REGULATORY AGENCY INSPECTION	32
18.0	ETHICS/PROTECTION OF HUMAN SUBJECTS	33
18.1	Ethical Standard	33
18.2	Institutional Review Board/Ethics Committee	33

ABLATE	Post-Approval Study	
18.3	INFORMED CONSENT PROCESS	33
18.4	Subject Confidentiality	33
19.0	DATA HANDLING AND RECORD KEEPING	34
19.1	Investigator Records	34
19.2	Investigator Reports	35
19.3	Data Management Responsibilities	36
19.4	Study Records Retention	36
20.0	PROTOCOL AMENDMENTS	36
21.0	TERMINATION OF STUDY OR STUDY SITE PARTICIPCATION	36
22.0	LITERATURE REFERENCES	38
APPEND	IX A: ADVERSE EVENT DEFINITIONS	39

PROTOCOL SUMMARY

Title:

AtriCure Synergy RF Energy Lesions For Non-Paroxysmal Forms Of Atrial Fibrillation Treatment During Concomitant On-Pump Cardiac Surgery Post-Approval Study (or "ABLATE PAS")

Device:

The AtriCure Synergy Ablation System

•

Objective:

The primary objective of this post-approval study is to evaluate clinical outcomes in a cohort of patients treated during commercial use of the AtriCure Synergy Ablation System by physicians performing the Maze IV procedure.

Design:

This prospective, open label, multi-center, observational, single arm registry is designed to monitor the AtriCure Synergy Ablation System continued safety and efficacy during the peri-procedural and long term phase during commercial use in patients being treated for non-paroxysmal forms of atrial fibrillation (AF) who are undergoing a concomitant open, on-pump cardiac surgical procedure.

Primary Efficacy
Outcome:

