The proportion of patients free from AF (i.e. no episodes lasting > 30 continuous seconds duration of either Atrial Fibrillation, Atrial Flutter or Atrial Tachycardia) while off Class I and III antiarrhythmic drugs for at least 4 weeks (except amiodarone which must be 12 weeks prior to assessment), as determined by an independent core lab assessment of 48 hour Holter, Zio[™] Patch or PPM interrogation recording performed at a minimum of 12, 24 and 36 months postoperatively (hypothesis test at 36 months).

Primary Safety
Outcome:

[figure not shown]
The proportion of patients with any serious device or ablation procedure-related adverse events
 within 30 days post-procedure or hospital discharge (whichever is later) as adjudicated by a Clinical Events Committee.

Secondary Efficacy Outcome:

The proportion of patients free from AF, regardless of AAD usage (i.e. no episodes lasting > 30 continuous seconds duration of either Atrial Fibrillation, Atrial Flutter or Atrial Tachycardia), as determined by an independent core lab assessment of 48 hour Holter, Zio™ Patch or PPM interrogation recording performed at a minimum of 12, 24 and 36 months postoperatively.

Secondary Safety Outcomes:

- Composite major adverse event: Serious adverse events occurring post-operatively within 30 days post-procedure or hospital discharge (whichever is later) including:
 - Death (includes deaths after 30 days or hospital discharge if death is procedure related).
 - Stroke (resulting in significant permanent disability)
 - o TIA
 - Myocardial infarction, and
 - Excessive bleeding (requiring >2 units of blood replacement and surgical intervention).

 Pacemaker implantation (PPM) within 30 days post procedure will be summarized and reported by reason for PPM (i.e., sinus node dysfunction, AV-node, etc.).

Planned Enrollment:

Up to 390 subjects.

Population:

Subjects who have non-paroxysmal forms of AF and are scheduled to undergo a primary open cardiac surgical procedure requiring cardiopulmonary bypass including valve surgery and/or CABG.

Follow-up Schedule: All patients will undergo clinical follow-up in hospital and at 30 days,

4, 12, 24 and 36 months post procedure.

Number of Sites: 50 study centers located in North America

Study Duration Study Start: Q3/2012

(Estimated): Enrollment Completion: Q4/2014 Follow Up Completion: Q4/2017

Final Report: Q2/2018 (See detail in section 6.5)

Inclusion Criteria:

[figure not shown]
• Age ≥ 18 years.

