16.4 Safety

The primary safety objective of the ABLATE Post Approval Study (ABLATE PAS) is to demonstrate that the serious device and ablation procedure related AE rate (excluding pacemaker implantation) within 30 days or prior to discharge (whichever is later) of the AtriCure Synergy Ablation System is no worse than a performance goal derived from the non-paroxysmal AF subject cohort of the combined AtriCure IDE ABLATE and ABLATE AF clinical trials.

The rate of serious device or ablation procedure related adverse events (excluding pacemaker implantation) within 30 days or prior to discharge (whichever is later) in the non-paroxysmal AF subject cohort of the combined AtriCure IDE ABLATE and ABLATE AF clinical trials was 6.25% (4/64).

The acceptable upper limit of the serious device and ablation procedure related AE rate for the ABLATE PAS trial (i.e. the performance goal) is established at 10%.

The primary safety hypotheses for this study are stated as follows:

 $H_0: \pi_{PAS_SAFETY} \ge 10\%$ $H_1: \pi_{PAS_SAFETY} < 10\%$

Using a one-sided exact binomial test for proportions at the 0.05 overall level of significance, a total of 333 subjects are required to demonstrate that the 30 day serious device or procedure related AErate

(excluding pacemaker implantation) in subjects treated with the AtriCure Synergy Ablation System is < 10% (the performance goal) with 80% power. This calculation was completed using PASS 2008 Power and Sample Size Software by NCSS.

A maximum of 15% Loss to Follow-Up (LTFU) is anticipated through 30 days, as such the sample size for enrollment is increased to 390 subjects to ensure a minimum of 333 subjects are available for assessment of the primary safety endpoint through 30 days. Should LTFU be less than 15%, enrollment will stop early given the safety endpoint is powered to at least 80%.

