Pseudo-aneurysm: Disruption of the arterial wall characterized by an outpouching or pocket with swirling, flowing blood outside of the confines of the arterial lumen.

Respiratory failure: Need for mechanical ventilation beyond 48 hours of completion of surgical procedure(s), or the need for re-intubation and ventilator support occurring at any time within 30 days of the surgical procedure, outside the setting of an additional operation.

Renal failure: a.) Increase of > 2.0 mg/dl in serum creatinine from any previous value or, b.) \geq 50% increase over baseline to a level that is \geq the upper limit of normal which may require dialysis. .

Reoperation: A repeat operation for the same condition in the same patient or to resolve an adverse event resulting from the initial operation. Reoperation is not an adverse event – it is an outcome – the reason for reoperation is the adverse event.

Restrictive (constrictive) pericarditis: A *chronic* form of *pericarditis* in which the pericardium is rigid, thickened, scarred, and less elastic than normal. The pericardium cannot stretch as the heart beats, which prevents the chambers of the heart from filling.

Retroperitoneal bleeding: Documented collection of blood in the retroperitoneum or by CT/MR.

Sepsis: Positive blood cultures associated with cardiovascular collapse and signs and symptoms of multiorgan failure.

Septicemia: Positive blood cultures.

Seizures: Sudden, uncontrolled muscle spasms with or without loss of consciousness resulting from brain electrical activity.

Sick sinus syndrome: Also called **sinus node dysfunction**, is a group of abnormal heart rhythms (arrhythmia) presumably caused by a malfunction of the sinus node, the heart's primary pacemaker, often resulting in the combination of sinus bradycardia alternating with rapid supraventricular rhythms such as afib with rapid ventricular response, as tachycardia-bradycardia syndrome

Stroke (permanent disability): A loss of brain function that occurs when the blood supply to any part of the brain is interrupted, resulting in tissue death or that which occurs with cerebral hemorrhage with clinical sequelae lasting more than 24 hours. Clinical signs/symptoms of neurological deficit as determined by standard comprehensive neurological examination, neurological imaging (CT scan or MRI) or autopsy.

May be further categorized as:

- **Ischemic Stroke:** Neurologic deficit attributed to thromboembolic event.

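### The pacemaker summary stops at day 30: in-hospital implants after that fall outside both the tested safety rate and the by-reason summary, and no later pacemaker count is planned

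*Combined protocol and SAP*

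**What the plan says.** Three places define the pacemaker item, and all stop at day 30. Section 12.2 governs collection: "Information regarding PPM implantation within 30 days of the procedure will be collected and documented in the CRF, including time of implant and reason". Section 7.4 governs reporting: "Permanent Pacemaker Implantation (PPM) occurring within 30 days post procedure will be" summarized by reason. The Protocol Summary agrees: "Pacemaker implantation (PPM) within 30 days post procedure will be summarized and reported by reason for PPM". None of them extends the window for a longer hospital stay.

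The neighbouring acute outcomes do extend it. Section 7.3 sets the primary safety window as "within 30 days post-procedure or hospital discharge (whichever is later"), and the composite in Section 7.4 uses the same rule. Section 16.4 defines the rate that is tested as "excluding pacemaker implantation) within 30 days or prior to discharge (whichever is later").

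On the longer term, the Protocol Summary describes a registry that monitors "continued safety and efficacy during the peri-procedural and long term phase during commercial use", with visits to 36 months. Section 2.0 says the study is a condition of approval, meant to collect acute and longer-term outcomes. The serious adverse event paragraph in Section 7.4 states its aim as "to provide a complete profile of the acute and long-term safety of the device and procedure".

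**The concern.** Once Section 16.4 takes pacemaker implantation out of the tested rate, the secondary pacemaker item is the only place in the plan where implants are counted by reason. Its window is shorter than that of the outcomes beside it, and it closes at the start of a three-year follow-up. Section 12.1, directly before it, collects any repeat catheter ablation or cardioversion with no time limit, so the day-30 cut is specific to pacemakers.

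Two things are at stake. The acute pacemaker figure would not match the acute safety window for patients with long stays. And the study would end without a planned cumulative pacemaker figure by reason; anyone wanting one would have to rebuild it from individual adverse event records.

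**Working it through.** **1. The plan's own figure.** Inputs from Section 16.4: performance goal 10%, assumed rate 6.25% (4/64), one-sided exact binomial test at 0.05, 80% power, 333 subjects. Take the largest c with P(X ≤ c | n = 333, p = 0.10) ≤ 0.05. This gives c = 24, with probability 0.0492. Power is P(X ≤ 24 | n = 333, p = 0.0625) = 0.801. The stated 333 reproduces. Pacemaker implantation is outside this rate, so changing the pacemaker window alters neither the test nor the sample size.

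**2. The windows side by side.**

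| Time of implant | Tested safety rate (16.4) | By-reason pacemaker summary (Protocol Summary, 7.4, 12.2) |
|---|---|---|
| Up to day 30 | In the window, but excluded | Counted |
| After day 30, before discharge | In the window, but excluded | Outside the window |
| After day 30 and after discharge, to month 36 | Outside the window | Outside the window |

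The second row is an internal gap. The third row would be outside the tested rate with or without the exclusion; what is missing there is any planned pacemaker count.

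**3. Whether general safety reporting fills the gap.**
- Section 13.1 requires all adverse events to be reported. Section 13.3 exempts sinus bradycardia only if it needs no treatment or intervention. Section 13.4 makes an event that requires hospitalization serious. So the event behind a late implant should reach the database.
- Section 7.4 specifies the interval summary by seriousness and attribution, not by intervention. A pacemaker count cannot be read from it.
- Section 16.6 adds a 1-year rate, but only for serious device- or ablation-related events. It ends 36 − 12 = 24 months before follow-up does, and it does not say whether the pacemaker exclusion applies.
- Appendix A has entries for significant bradycardia and sick sinus syndrome, but none for pacemaker implantation. It says of another intervention, "Reoperation is not an adverse event", and codes the reason instead. By analogy only, since the text does not say this of pacemakers, a late implant would sit under its cause together with cases that were never implanted.

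**4. Whether interrogation fills it.** Pacemaker interrogation is an accepted efficacy recording at 12, 24 and 36 months, but it reveals a device only in patients assessed that way. Section 9.1 accepts pacemaker recordings as baseline evidence of AF, and Section 9.2 does not exclude a prior pacemaker. Interrogation alone therefore cannot separate new devices from old ones or supply the reason.

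**5. Size.** The documents give no pacemaker rate, no timing of implants and no number of stays beyond 30 days, so the number affected cannot be computed. For scale only, each 1% of patients implanted after day 30 would be 333 × 0.01 = 3.3 of the safety sample, or 250 × 0.01 = 2.5 of the 250 whom Section 16.5 takes as evaluable at three years. The window covers 30 / (3 × 365) = 30 / 1,095 = 2.7% of follow-up time. That is calendar time, not a share of implants.

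**The case against.** A reader might infer that pacemaker implantation goes unrecorded after day 30. The documents do not support that. Sites report adverse events throughout, bradycardia needing intervention is not exempt, and serious events are summarized at every interval.

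A reader might also infer that the plan breaks a promise of a 36-month pacemaker rate. It makes no such promise: the phrase about a complete acute and long-term profile closes the paragraph on serious adverse events, and that summary is the stated means. Nor can it be said that the 30-day figure understates anything; it is labelled as a 30-day figure, and no late rate is available for comparison.

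It can further be said that the 30-day limit is consistent in all three places, that the item is descriptive, and that a late pacemaker rate in a single-arm study with concomitant valve or bypass surgery has no comparator. The public text also lacks the opening of Section 12 and any visit schedule, and Section 16.2 defers some detail to a statistical analysis plan, so pacemaker items at later visits cannot be ruled out.

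These points narrow the finding and lower its weight. They do not supply the missing extension to discharge, and none of them shows a planned pacemaker count after day 30.

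**Conclusion.** The point holds in a limited form. As written, an implant after day 30 but before discharge is in neither the tested rate nor the by-reason summary, and no pacemaker count or by-reason rate is planned after day 30 in a study followed to 36 months. The underlying events should be captured; the count of implants is what is missing. The number of patients affected is unknown, and the primary safety conclusion is not at risk.

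Two assumptions matter. First, the Section 16.4 exclusion is taken to govern the test, although Sections 7.3 and 16.6 do not repeat it. If it did not govern, a serious related event involving an implant between day 31 and discharge could enter the tested rate, and the acute gap would shrink to the by-reason summary. Second, no later pacemaker item is taken to exist in the parts of the schedule not shown. If one does, collection is already in place and only the wording and the table need to change.

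**What to change.** - In the Protocol Summary, Section 7.4 and Section 12.2, give the acute pacemaker item the same window as the primary safety outcome in Section 7.3.
- In Section 12.2, keep the existing form item (implant date and reason, with the site's attribution under the Section 13.2 categories) open at the planned 4-, 12-, 24- and 36-month visits.
- Add a descriptive cumulative table by reason at 12, 24 and 36 months among patients without a pacemaker at baseline, showing the number still in follow-up at each time.

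The Clinical Events Committee's 30-day review need not be extended, and the primary safety test and its sample size stay as they are. The cost is slightly more data entry at visits already planned, one more table, and a pacemaker figure that may be higher than the 30-day one. Baseline pacemaker status is needed for the denominator; if the medical history form does not already record it, that is one further field.
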